#### 1.7.2.8 *Pharmacokinetic Evaluations*

Plasma will be collected to measure compliance and further assess the pharmacokinetic profile of ALK-001, how it might be influenced by dietary vitamin A intake, how it fluctuates over a 2-year period as liver stores are turned over, and how the percentage of deuterated vitamin A in the blood might be linked to the progression of GA.

Metabolites of vitamin A measured in this study: ALK-001 is expected to replace existing, non-deuterated vitamin A. Total vitamin A in the plasma will be approximated by the sum of retinol + retinyl palmitate. Levels of deuterated retinyl palmitate peak 4 hours following administration of one ALK-001 dose then rapidly return close to baseline levels 24 hours post-dosing. Levels of deuterated retinol increase more slowly to peak 8-12 hours following dosing and decrease more slowly over time. Retinoic acid, another vitamin A metabolite with direct function on vision, will be measured. The absolute levels and percentage deuteration of retinol, retinyl palmitate and retinoic acid will also be measured. Percentages are calculated as the ratio between the deuterated analyte and the total amount of each analyte. Total amounts of each analyte will be calculated as the sum of the deuterated and the non-deuterated analyte. Absolute levels above the upper limit of normal may not indicate toxicity in the absence of clinical signs or other clinically meaningful laboratory abnormalities.

Levels of each analyte are expected to remain below the following upper limit of normal, determined based on a review of the literature:

Analyte (total deuterated + non-deuterated)	Approximate upper limit of normal
Retinol	1,500 ng/mL
Retinyl palmitate (random)	5,000 ng/mL
Retinyl palmitate (12+ hour after dosing)	500 ng/mL
Retinyl palmitate (24+ hour after dosing)	200 ng/mL
Retinoic acid (random)	5 ng/mL

#### 1.7.2.9 *Efficacy Evaluations*

Effects of ALK-001 on the progression of GA will be evaluated using fundus autofluorescence imaging. Although atrophic lesions can be readily measured using FAF imaging, OCT imaging will be used to confirm that the measured areas are indeed atrophic regions of the retina.

In addition, other measures of efficacy will be explored by measuring the following variables:

- Incidence of CNV,
- BCVA,
- Reading speed,
- Visual questionnaires, and
- Microperimetry (at sites where available).

### 1.7.2.10 Complement and Genotype (Optional)

**This section is optional and may be revised.** We propose to explore the association between each subject's response to ALK-001 and their complement status, as determined by *genetic polymorphisms (SNPs, serum levels, and complement function* (synonym of "activity"). Studying the complement in this study is relevant because vitamin A dimers are known to activate the complement cascade [20, 30]. Studies have shown that inhibiting dimerization in mouse leads to normalization of the transcription of genes involved in the complement [85].

The complement system comprises approximately 20 proteins synthesized by the liver and the RPE [86]. AMD risk is associated with DNA variants for the genes encoding for complement system proteins. For example, complement factor H (CFH) is strongly associated with AMD [53-56], with a single common variant explaining ~43% of AMD risk in older adults. Common genetic variants in complement component C3, Factor B, C2, and Factor I also confer a risk for the disease [87]. In contrast, certain mutations spanning CFH confer protection from developing AMD [88, 89]. Genetic testing can give information about the risk of developing AMD, but to date there have been no solid associations between genetic mutations and severity of geographic atrophy progression, or response to therapeutic intervention [90-92]. To address this shortcoming, this study will carry out genetic testing and quantification of serum complement proteins, and in addition will test the actual function (see table below) of the complement system in each patient, as genetic variants may result in differences in complement function even in absence of gene expression differences. As complement function is constant over time [93, 94], and complement is expected to function similarly in the retina, complement function in the plasma will be measured using the commercial CH50 and AH50 tests.

We suspect that vitamin A dimers, which form on the surface of the phospholipids of the disk membranes, modify disk membranes in ways that activate complement. Such complement activation caused by vitamin A dimer-modified disk membranes would explain data linking vitamin A dimers to complement. Such a scenario would also predict that patients whose complement system reacts more strongly to dimer-altered disk membranes would most benefit from preventing such alteration through administration of ALK-001. We thus plan to evaluate complement status as a means to predict the extent to which patients may benefit from ALK-001. We will search for a correlation between complement serum levels and/or genetic polymorphisms of approximately 20 AMD-associated genes, and/or, complement function with treatment effects measured as GA growth rates.

Accordingly, we may collect blood or saliva samples from participants in order to test the following (list may be revised in a separate document without amending this protocol):

**(1)** Complement function will be measured using two commercial assays:

Test Name	Notes	Range	Ref.
Complement, Total, function (CH50)	Measures the ability of the membrane attack complex to form and lyse altered liposomes decorated with foreign dinitrophenyl groups.	30-75 U/mL	[95]
Complement, Alternate (AH50)	Activates serum then quantifies formation of the C5b-9, membrane attack complex, via the alternative pathway	>46%	[96]

**(2)** Complement serum levels of C3d, Ba, C3a, C5a, SC5b-9, C3, C4, factor B, factor H and factor D will be quantified.

**(3)** Complement genetic polymorphisms (SNPs) of 20 genes associated with AMD will be tested by a CLIA-certified lab. The genes include: ABCA4, C2, C3, CFB, CFH, CFI, CNGB3, CST3,

CX3CR1, EFEMP1, ELOVL4, ERCC6, FBLN5, HMCN1, HTRA1, PRPH2, RAX2, RLBP1, RPGR, TLR4, as well as ARMS2 individually. This list may be amended by sponsor.

We may compare 1) Complement function; and/or 2) Complement serum levels and 3) Complement genetic polymorphisms (SNPs with rates of GA growth as determined by FAF, in order to determine the extent to which any of these variables is predictive of those AMD patients most likely to benefit from ALK-001.

#### *1.7.2.11 Avoidance of vitamin A supplements and liver products during the trial*

Because ALK-001 replaces vitamin A, any overly high intake of dietary vitamin A will reduce the activity of the drug. Study participants should avoid consumption of vitamin supplements containing vitamin A or beta-carotene, and liver-based products (liver, liver oil, liver sausage, etc.). Consumption of fruits and vegetables is not restricted. See section [1.11.2](#) for details.

## **1.8 SUBJECT SELECTION**

### **1.8.1 Inclusion Criteria**

A prospective subject will be eligible if he/she meets all the following inclusion criteria at screening or at randomization (as applicable), except upon sponsor's approval which shall be documented:

#### *General inclusion criteria:*

1. Male or female, 60 years and older.
2. Healthy as judged by principal investigator.
3. Has signed and dated the informed consent form.
4. Is able and willing to perform the study procedures.
5. Is able and willing to comply with the schedule of the study visits.
6. Is able and willing to self-administer the study drug.
7. Is able and willing to follow the instructions and comply with the avoidance of vitamin A supplements.
8. Is likely to complete the 2-year study as judged by principal investigator.

#### *At least one eye, designated as the “study eye,” must meet all the following inclusion criteria:*

9. Study eye displays GA lesion(s) measuring a total area between approximately 1.5 sqmm and 20 sqmm (between ~0.5 and ~9 Disc Areas), measured on fundus autofluorescence imaging (FAF), as confirmed by sponsor.
10. Study eye presents hyperautofluorescent patterns in the junctional zone of GA.
11. If GA lesions are multifocal in the study eye, one lesion at least must be approximately 1.00 sqmm or greater.
12. In case of foveal sparing in the study eye, the smallest distance between GA border and foveal center must be less than approximately 250 µm.
13. All GA lesions in the study eye must fit entirely within the 30-degree retinal imaging field centered on the fovea.
14. Study eye has BCVA of 33 letters (~20/200) or better.
15. Study eye has clear or adequate ocular media and pupillary dilation, including no allergy to dilating eyedrops, to permit good quality retinal imaging.

#### *The non-study eye, designated as the “fellow eye,” must meet the following inclusion criterion:*

16. Fellow eye presents with at least one of the following features:

- (a) reticular pseudodrusen (RPD),
- (b) intermediate AMD with at least one macular drusen greater than approximately 125  $\mu\text{m}$  in diameter,
- (c) active or history of CNV, or
- (d) geographic atrophy with or without a history of, or concurrent CNV.

### 1.8.2 Exclusion Criteria

A prospective subject will **not** be eligible if **any** of the following criteria apply at screening or at randomization (as applicable), except upon sponsor's approval, which shall be documented:

#### General exclusion criteria:

17. Active or historical medical condition (systemic or ophthalmic), which in the opinion of the principal investigator, may prevent performance of study procedures, compliance with the protocol, or continuous participation of the subject throughout the 2-year duration of study.
18. Currently taking or has taken medications associated with retinal toxicity, except for short durations as judged by principal investigator.
19. Is currently taking and is unwilling or unable to discontinue oral retinoids or medications that might affect absorption, metabolism, or function of vitamin A.
20. Has participated in any drug or device trial within 60 days of randomization.
21. Anticipates participating in any other drug or device trial over the next 2 years.
22. Is hypersensitive or allergic to fluorescein.
23. Has clinically-significant abnormal laboratory result(s) at screening, which in the opinion of the principal investigator, makes the patient unsuitable for study participation.
24. Has clinically-significant abnormal physical exam finding(s) at screening, which in the opinion of the principal investigator, makes the patient unsuitable for study participation.
25. Has active or historical, acute or chronic, liver disorder except when benign.
26. Has a clinically-significant cardiac abnormality, a clinically-significant abnormal ECG, or a marked prolongation of QTc at screening (>460 ms for male or >480 ms for female, approximately).
27. Female of childbearing potential, pregnant, lactating or positive serum pregnancy test at screening.

#### Study eye exclusion criteria:

28. Study eye has historical or active CNV.
29. Study eye has refraction higher than 6 diopters (positive or negative) approximately, except if retinal imaging can be properly focused.
30. Study eye has GA thought or proven to be caused by any condition other than AMD.
31. Study eye has GA lesions expected to (i) expand larger than the imaging field of view, or (ii) merge with other retinal features (optic disc or peripapillary atrophy, other non-AMD atrophic lesions, etc.) during the 2 years of the study.
32. Subject, in the case of a systemic treatment, or study eye, in the case of a monocular treatment, has previously received treatment, surgery or procedure for GA or AMD, including clinical trials, except when there is documented evidence that the subject was receiving placebo or was part of a sham group.
33. Study eye has active or history of ocular disorder, which may confound assessment of the retina morphologically or functionally, as judged by principal investigator.
34. Study eye has uncontrolled elevated intraocular pressure, retinal detachment, RPE tear, recurring uveitis, retinal vein occlusion, diabetic retinopathy, diabetic macular edema.

35. Study eye has history of submacular surgery, any surgical intervention for AMD, vitrectomy, or device implantation (except IOL).
36. Study eye has received intravitreal injections or cataract surgery within 90 days of randomization.
37. Study eye is expected to require cataract, epiretinal membrane, or ocular surgery over the next 2 years as judged by principal investigator.

**NOTE:** PI shall make the final determination regarding all eligibility criteria.

### **1.8.3 Study Requirements, Restrictions and Instructions for Subjects**

Investigator should enroll participants they believe will follow the study requirements and be likely to complete the 24-month treatment period. Investigator shall discuss with prospective and enrolled subjects about the importance of the study requirements outlined below. Subjects must be willing and able to continuously adhere to the study requirements throughout the duration of the study. Non-compliant subjects may be withdrawn from and discontinue the study, and have to interrupt the study treatment. Details about each of the below requirement are found in the corresponding section.

1. **Adherence to visit schedule:** subjects will be informed about the schedule of all future visits and should ensure they have the time to participate in the 24-month study, and they are able to travel to/from the sites. Missed visits may result in withdrawal.
2. **Study procedures:** subjects should be informed of which study procedures will be performed.
3. **Compliance with study drug intake:** subjects should be informed before the study, and reminded during the study, to take the drug daily for 24 months, preferably at the same time every day and at the same time they take their other medications, unless prescribed otherwise by the investigator.
4. **Subjects must not consume dietary supplements containing vitamin A, liver-based products, or foods known to contain excessive amounts of vitamin A** (section 1.11.2).
5. **Subjects should not take any medications prohibited under this protocol**, except when medically indicated, for the duration of the study (section 1.11.3).
6. **Subjects must not enter into any other investigational drug or device clinical study**, unless deemed medically necessary by the PI and sponsor.
7. **Subjects must not become pregnant during the study.**

### **1.8.4 Exemptions to Entry Criteria**

Subjects must be compliant with all inclusion and exclusion criteria, unless an approvable exception is granted by sponsor according to section [1.17.12](#).

## **1.9 STUDY DRUG ADMINISTRATION AND MANAGEMENT**

### **1.9.1 Treatment Groups**

Subjects will be considered “enrolled” when they are determined to have met all eligibility criteria **and** after they are randomized to a treatment group. Subjects will be randomized 2:1 to ALK-001 or placebo. The treatment period will last 24 months and subjects and investigator will be masked to treatment group.

### **1.9.2 Timing of study drug intake**

- a) Subjects will be instructed to take one capsule per day, by mouth, at a time of their preference, preferably at the same time they take their other daily medications.
- b) Subjects will be instructed to take the study drug at approximately the same time each day.

- c) Time of usual study drug intake, duration elapsed since last study drug intake (at the time blood samples are collected during follow-up visits), and whether the capsule is taken before, after or during a meal should be recorded.

### 1.9.3 Missed Dose

- a) Subjects should avoid missed doses.
- b) If a subject forgets to take a dose, they should take the missed dose as soon as they remember it, even if that means taking 2 doses on the same day.
- c) Subjects should not take more than 2 capsules in one day.

### 1.9.4 Method of Assigning Subjects to Treatment Groups

#### 1.9.4.1 Randomization

Only after receiving authorization to do so by the sponsor, investigator will randomize subjects who have been confirmed to meet all entry criteria at the beginning of the run-in period and since then have not had any clinically-significant changes in health, which in the opinion of the principal investigator, would make the subject unsuitable to continue participation in the study. Randomization consists in assigning a medication ID to a subject and dispensing the study drug, usually on the same day. Subjects are allocated treatment by block.

#### 1.9.4.2 Errors in Medication ID assignment

If a subject is assigned a medication ID in error (except for placebo during run-in period and has not started treatment, the error shall immediately be corrected and documented, so that the subject receives the medication he/she was supposed to receive.

If a subject has already been dispensed and has already taken one capsule of the wrong medication ID, the drug dispensed medication ID shall now prevail and should replace the medication ID originally intended to be dispensed.

No two subjects shall be assigned the same medication ID (except during run-in period, and if such dispensing error has been made, the subject receiving the wrong medication shall be informed to immediately stop taking the wrongly provided medication, return all provided medication, and start receiving the proper medication. Randomization date shall be adjusted to the date at which the subject started the proper medication. A note should be added to the source documents to explain the discrepancy. If this dispensing error results in insufficient study drug available for a given subject, refer to section [1.9.8.2](#).

#### 1.9.4.3 Randomization Process

A randomization list is used to select which medication ID to dispense to each subject. The investigator must pick the next medication ID available at the clinical site, by following the order on the masked randomization list that will be distributed at the start of the trial, or by using an Interactive Web Response System (IWRS for randomization. Sponsor will be responsible for ensuring that study drug supplies are delivered to each site. Investigators should inform sponsor in advance of subjects' scheduled randomization visits, so that sufficient drug supply is already at the site on the scheduled day of randomization.

Once randomized, subjects will immediately receive the applicable study drug either through PI or designated personnel, through site pharmacy, or directly by mail. If received by mail, subjects will be requested to confirm receipt, which shall be documented.

#### 1.9.4.4 *Randomization code, randomization list (or schedule):*

A randomization code, used to prepare the randomization list, will first be prepared by the sponsor. The code will be programmed to be reproducible if the need arises. Once approved, this code will be tested by sponsor to generate a dummy randomization list for quality control. Once the code has been verified to meet protocol requirements, an unmasked vendor/consultant designated by the sponsor will generate the final randomization lists (masked and unmasked). The *unmasked* randomization list will be accessible to select persons only (SMC members, unmasked statistician(s, label printing company, packaging company, other unmasked organizations. The investigator and the sponsor will receive a copy of the *masked* randomization list which will contain the sequence of medication IDs, but not the actual treatment allocation nor any information about blocks order or size. Any further instructions for randomization will be provided separately.

#### 1.9.5 **Treatment Allocation**

To assure even treatment balance and minimization of bias, subject allocation to treatment group will be determined using random permuted block randomization, without stratification. The following tables summarize the expected enrollment:

Treatment Group	Total
Placebo	100
ALK-001 14 mg/day	200
Total	300

#### 1.9.6 **Dose Modification or Interruption**

Except when approved by sponsor or as permitted in other sections of this protocol, modifications of the study drug dosage are prohibited, including if subject has received the incorrect drug dose by mistake. If study drug dosing must be interrupted (see 1.14.4), the subject may be discontinued from the study after discussions with the sponsor (see 1.14.6).

#### 1.9.7 **Masking / Unmasking**

##### 1.9.7.1 *Masking to Treatment Assignment*

Subjects, site personnel, pharmacy personnel, monitors and sponsors will remain masked to the treatment assignments throughout the study, except as provided in 1.9.7.3. The below list provides a list of personnel involved in the study and whether they should be masked to treatment ("M" or unmasked to treatment ("U". If necessary for the conduct of the study, this list might be amended by the sponsor and if so, will be documented in the regulatory binder. The list of persons authorized to receive unmasked data/treatment code may be amended from time to time by the sponsor.

	Treatment assignment	Bioanalytical data
Sponsor personnel with direct or indirect access to clinical data (Coordinating Personnel)	M	Available, masked to treatment and subject ID
Site study team (including PI, sub-I, coordinator)	M	Available, masked to treatment and subject ID
Site pharmacy (if applicable)	M	-
Monitor	M	Available, masked to treatment and subject ID
Central Lab	M	-
Reading Center (Retinal Imaging)	M	-
Bioanalytical laboratory	M	U
Study drug supply management designee	U	-
Quality assurance person / Unmasked monitor	U	U
SMC	U	U
Statistician preparing unmasked analyses	U	U
Designees preparing randomization list	U	-

- does not have access to data  
**M** masked to treatment  
**U** unmasked to treatment

#### 1.9.7.2 Masking to PK data

For each subject in the trial, the bioanalytical lab or an unmasked person may generate and assign a random subject PK ID to each subject (which will be different from the medication ID or the actual subject ID). This is to mask the subject ID from the clinical team and sponsor, but still be able to provide individual data to masked personnel.

Full, identifiable results containing subject IDs, site, treatment allocation, or blood collection date can only be provided to authorized personnel, which shall include at least the SMC, statisticians and unmasked personnel designated by the sponsor.

Sponsor and investigators should be allowed to review PK data on an-ongoing basis as long as such data does not enable treatment unmasking. The bioanalytical lab or a designated unmasked person will be in charge of reviewing the PK data and/or providing a redacted version to the sponsor and investigators.

For that, all pharmacokinetic data and treatment assignment (active dose vs. placebo) will be made available, but will not contain the subject's identity (i.e. subject ID number, medication ID, nor the dates of visit, specific site, or any other information that could result in unmasking or partial unmasking of the treatment allocation). The table should contain the masked subject PK ID. Furthermore, datasets shall be provided only in bulk following the randomization block, or as determined appropriate by the statistician. Special precautions should be taken after subjects are withdrawn from the study, or for subjects with missed data/visits to avoid unmasking. Such precautions shall be put in place by the designated person providing the data to the sponsor and investigators.

Hypothetical example of bioanalytical table that can be sent to masked personnel:

Subject ID	Subject PK ID	Collection Date	Collection Time	Retinol Conc. (ng/mL)	Retinol-d 3 Conc. (ng/mL)	Visit
	001			380	0	V01
	001			80	400	V03
	001			40	450	V04
	002			520	0	V01
	002			80	450	V03
	002			35	500	V04

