#### *1.7.2.7 Safety Evaluations*

Based upon vitamin A's known safety and tolerability profile, possible AEs of interest have been identified and will be monitored during this study (see section [1.5.8.1](#)). Safety data will be acquired by: 12-lead ECG, physical exam, ocular exams, retinal photographs, clinical laboratory tests, bioanalytical tests (vitamin A), BCVA.

To make sure that any potential for hypervitaminosis A is detected, *symptoms* such as headaches, nausea, dry lips, dry skin, *signs* such as papilledema (optic disc swelling), and clinically meaningful abnormalities

in clinical laboratories will be explored (see section 1.16.1.6). In addition, levels of retinol, retinoic acid, and retinyl esters will be measured periodically. In order to avoid study unmasking, such data will be reviewed by the SMC. See section below on pharmacokinetic evaluations.

Vitamin A-related adverse reactions are usually reversible upon discontinuation of the vitamin.

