3.1. Overall Study Design

This is a randomized, double-masked, parallel-group, multicenter study evaluating the safety and efficacy of ALK-001 in subjects with GA secondary to AMD.

Approximately 300 subjects were planned to be randomized in a 2:1 ratio to receive either ALK-001 at 14 mg/day or placebo daily for a total treatment duration of 24 months. There was no stratification for randomization, and subjects were randomized using random permuted blocks of size 3 and 6. Due to enrollment delays caused by COVID-19, 200 subjects were randomized with the same 2:1 randomization. Subjects, investigators and study staff, and sponsor staff who may be in contact with investigators or subjects, are masked until after this SAP is submitted to FDA and database lock has occurred.

After an initial screening day (V01), subjects are given a placebo to take once a day during a run-in period. The placebo is indistinguishable from ALK-001, and subjects are unaware that they are receiving the placebo. The run-in period typically lasts between 2 and 4 weeks. At the conclusion of the screening and run-in period, subjects who meet all eligibility criteria were randomized on Day 1 (V02).

Following randomization at V02, subjects have follow-up visits scheduled at Month 6 (V04), Month 12 (V06), Month 18 (V08), and Month 24 (V10) after starting treatment on Day 1. Treatment discontinues at Month 24 (V10). A diagram of the study design and timelines is provided below.

The follow-up visits encompass various assessments. Safety and tolerability will be assessed by monitoring AEs, clinical laboratory tests (biochemistry, hematology, lipids), vital signs, ECG, physical examinations, and pharmacokinetics. Efficacy assessments include GA area measured on FAF imaging, BCVA, LLVA, reading speed, VFQ-25, FRI, microperimetry (optionally performed at sites where available), etc. (Refer to [Appendix 1](#) for a full list of assessments and visit schedule).

Each subject's study duration is up to 2 years and 4 weeks, including screening and run-in period and the 2-year treatment. The study will end when the last subject completes Visit V10 (Month 24) or discontinues the study.

Following completion of the initial treatment period of 2 years, subjects may be given the choice to enter a two-year open-label extension study, which is not covered in this SAP.

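### Protocol 1.9.7.2 offers masked staff per-subject PK data with treatment assignment during the trial, contradicting the masking table in 1.9.7.1

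*Protocol*

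**What the plan says.** All protocol references are to version 1.1.

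- **Protocol 1.9.7.1.** Subjects, sites, monitors and sponsor "will remain masked to the treatment assignments throughout the study, except as provided in 1.9.7.3". Section 1.9.7.3 covers unmasking of individual subjects in a medical emergency. In the table, sponsor personnel with access to clinical data, the site team and the monitor are masked to treatment, and their bioanalytical entry reads "Available, masked to treatment and subject ID".
- **Protocol 1.9.7.2.** "Sponsor and investigators should be allowed to review PK data on an-ongoing basis as long as such data does not enable treatment unmasking". For that purpose, "all pharmacokinetic data and treatment assignment (active dose vs. placebo) will be made available". Subject ID, medication ID, visit dates, site and anything else that could unmask are to be left out. Release is in bulk by randomization block, or as the statistician judges appropriate. Special precautions are required for withdrawn subjects and missed visits. Among full identifiable results, "treatment allocation, or blood collection date can only be provided to authorized personnel".
- **The sample table in 1.9.7.2**, introduced as "Hypothetical example of bioanalytical table that can be sent to masked personnel", has one row per PK ID and visit, retinol and retinol-d3 concentrations, a completed Visit column and no arm column.
- **Protocol 1.7.2.7**, on retinol, retinoic acid and retinyl ester levels: "In order to avoid study unmasking, such data will be reviewed by the SMC".
- **Protocol 1.12.13** lets the PI skip V03, V05, V07 and V09. SAP 8.0 requires a PK sample at every in-person visit except V02.
- **SAP 3.1**: "subjects were randomized using random permuted blocks of size 3 and 6"; 200 subjects were randomized 2:1; masking lasts until the SAP has gone to FDA and the database is locked.

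**The concern.** The table masks two things from these roles, treatment and subject identity. Section 1.9.7.2 masks only the second. A data provider following 1.9.7.2 would give masked roles something that 1.9.7.1 withholds, and the emergency provision in 1.9.7.3 does not cover it.

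Once the arm is visible for each PK ID, masking depends on nobody linking a PK ID to a subject. The recipients include people who know which subject attended which visit.

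The same groups measure BCVA and LLVA (the two key secondary endpoints) and reading speed, diagnose CNV by local standard of care, and take part in withdrawal decisions. The sponsor also decides Per Protocol membership (SAP 4.5) and corrects MNRead data by manual review (SAP 4.6.6). GA area is less exposed: it is graded centrally, and the masking table gives the reading center no bioanalytical data.

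**Working it through.** The documents give no figure on this point. The check has a textual part and an illustrative calculation.

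**1. The two sections side by side**

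| | Treatment | Subject identity |
|---|---|---|
| 1.9.7.1 table (sponsor, site, monitor) | masked | masked |
| 1.9.7.2 release (sponsor, investigators) | made available | masked |

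They differ in the treatment column. No assumption is needed for this.

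**2. Would dropping the arm column reconcile them?** No. Protocol 1.5.7.3 reports that 80% of plasma vitamin A was deuterated after 4 weeks on drug. In the sample table retinol-d3 is 0 at V01 for both PK IDs. The later deuterated fractions of retinol are:

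- PK ID 001: 400/(80+400) = 83% at V03, 450/(40+450) = 92% at V04.
- PK ID 002: 450/(80+450) = 85% at V03, 500/(35+500) = 93% at V04.

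Anyone holding the concentrations holds the arm.

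**3. How far could the Visit column help linkage?** Four optional visits give 2^4 = 16 attendance patterns. Assume each is attended independently with probability p and all major visits are attended. The documents give no attendance rates, so p runs from 0.1 to 0.9. For a pattern with probability q, the chance that a subject's pattern is unique in a release of n subjects is

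P(unique) = Σ q(1 − q)^(n−1), summed over patterns.

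At p = 0.5 every q is 1/16, so P = (15/16)^2 = 88% for n = 3 and (15/16)^5 = 72% for n = 6.

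At p = 0.1 the values of q are 0.6561 (1 pattern), 0.0729 (4), 0.0081 (6), 0.0009 (4) and 0.0001 (1). For n = 3 the terms are 0.0776 + 0.2506 + 0.0478 + 0.0036 + 0.0001 = 0.380. For n = 6 the sum is 0.253. By symmetry p = 0.9 gives the same.

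| Optional visits so far | Block of 3 | Block of 6 |
|---|---|---|
| V03 only (Month 6) | 9–25% | 3–6% |
| V03, V05 (Month 12) | 19–56% | 12–24% |
| All four (Month 24) | 38–88% | 25–72% |

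In one pooled release of 200, the Month 24 figure is 0–1.3%, or about 0 to 2.6 subjects.

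**4. Correlated attendance.** Section 1.12.13 ties skipping to travel burden, which tends to persist within a subject. In the extreme where a subject attends all or none (50/50), uniqueness is 2 × 0.5 × 0.5^2 = 25% in a block of 3 and 2 × 0.5 × 0.5^5 = 3% in a block of 6.

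**5. Arm revealed without a unique pattern.** A subject's arm is also exposed when every block member sharing the pattern is in the same arm. Simulating 20,000 blocks per setting under the independent-attendance model gives about 49–92% (block of 3) and 34–84% (block of 6) by Month 24, again only if block membership is known.

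**The case against.** The best defense reads the table entry as masked to the treatment of an identifiable subject. On that reading 1.9.7.2 describes how such data are supplied, and the two sections agree in purpose. Section 1.9.7.2 also has more safeguards than a substitute ID: review is conditional on not enabling unmasking, an unmasked reviewer or the lab may redact, dates and site are removed along with any other unmasking information, the statistician may choose another release unit, and missed visits are singled out for precautions. A reader might infer that the PK ID is the only protection; the section does not support that.

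This defense reduces the practical risk but leaves the conflict standing. The table names treatment and subject ID separately, and 1.9.7.2 releases the first. The precautions are not described, and the sample table shows the visit pattern they are meant to hide.

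Two further points are fair. A reader might infer that 1.7.2.7 reserves these data for the SMC. It says the SMC will review them, not that nobody else may, and the table itself marks bioanalytical data as available. It does, however, recognize that such data can unmask. Also, Protocol 1.9.4.4 withholds block order and size, and site is stripped from the release, so a recipient would have to infer who belongs to a block before a pattern unique within it points to anyone.

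**Conclusion.** The contradiction between 1.9.7.1 and 1.9.7.2 is real, rests on wording alone and should be corrected. It is an internal inconsistency with a possible consequence for masking.

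Linkage through visit patterns is possible, not shown. The upper figures of 88% and 72% might be taken as the chance that a subject is unmasked. They are not: they require known block membership, all four optional visits to have passed, independent attendance at 50%, and no effective precautions. Earlier releases, correlated attendance or pooling lower them, and one pooled release of 200 brings the figure to about 0–1.3%. Missed major visits and withdrawals are outside the calculation and would add some risk.

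A reader might also infer that assessors were in fact unmasked. The documents do not say that any such table was released. The wording of 1.9.7.2 is largely permissive, and SAP 3.1 states that staff remain masked until database lock. Central grading of GA area on FAF is protected in either case; the site-assessed endpoints and withdrawal decisions depend on the masking holding.

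**What to change.** - Reconcile 1.9.7.2 with 1.9.7.1 by deleting the release of treatment assignment to sponsor and investigators.
- Give masked staff no subject-level deuterated-analyte data before database lock. If they need PK information, supply at most pooled summaries without rows by PK ID and visit, and remove the sample table.
- Send subject-level PK only to the SMC, the unmasked statistician and the other roles listed as unmasked to these data.
- State in the CSR whether any subject-level PK tables reached masked staff and, if so, to whom, when and in what grouping. Randomization is complete and the SAP describes 80% of subjects as having completed the study, so new wording cannot undo an earlier release.

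The cost is small: a wording change, a short CSR statement, and the loss to masked staff of an ongoing subject-level view of PK and compliance. Capsule counts and phone calls (Protocol 1.10) remain for compliance, and the SMC keeps its review of vitamin A levels.
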